3.3 Dosing algorithm

The goal of the lead-in phase Ib is to determine the MTD and RP2D. We will first treat 6 patients at dose level 0 in the phase Ib. If DLT occurs in $\geq 2/6$ patients, this dose level would exceed the MTD, and 6 patients will be treated at the next lower dose level (i.e. dose level -1). If DLT occurs in $< 2/6$ patients at dose level 0, the next cohort of 6 patients will be treated at the next higher dose level (i.e. dose level +1). The dose escalation or de-escalation (Table 1) will continue in cohorts of 6 until we reach the highest dose level at which $< 2/6$ patients experience a DLT in the first 28 days. The highest dose level at which 0-1/6 patients experience a DLT in the first 28 days of treatment will be the MTD. The RP2D will be selected from among the doses evaluated after reviewing the efficacy, safety, pharmacodynamics data. The RP2D selected may be lower than the MTD. The RP2D will be used to treat an additional 20 patients in the phase II expansion portion of the study.

If $\geq 2/6$ patients experience DLT at dose level -1, the study may be revised to consider additional lower dose levels.

Patients that are removed from study before day 28 for any reason other than toxicity and have not experienced DLT will be replaced.

*With up to 1 potential dose escalation level (+1) to be studied and up to 6 patients to be treated at a given dose, the target maximum number of patients projected to be enrolled in the phase Ib part of the trial will be 12.

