3.4 Definition of dose-limiting toxicity (DLT)

DLT is defined as a grade 3 or higher, clinically significant non-hematologic adverse event or abnormal laboratory value assessed as unrelated to disease progression, intercurrent illness, or concomitant medications and occurring during the first cycle on study, with the following exceptions:

- Grade 3 or 4 nausea, vomiting, or diarrhea that can be managed to ≤ grade 2 with standard antiemetic or antidiarrheal medications used at prescribed dose within 7 days of onset.
- Electrolyte abnormalities of Grade 3 or higher which can be corrected to grade 2 or less within 48 hours will not be considered as DLT only if the abnormalities are asymptomatic and corrected by optimal replacement therapy within 48 hours. Symptomatic grade 3 or higher electrolyte abnormalities will be considered DLT even if correctable within 48 hours.
- Grade 3 or 4 biochemical abnormalities of amylase or lipase without evidence of clinical pancreatitis.
- Grade 3 or 4 anorexia or fatigue.
- Grade 3 QTc prolongation will constitute DLT as follows: The QTc interval will be calculated by Fridericia's correction factor (QTcF). If the QTcF is > 500 msec the EKG must be evaluated within 4 hours in triplicate and if persistent ≥ grade 3 QTc prolongation is confirmed this will be considered a DLT. Note: Grade 4 QTc prolongation will be considered a DLT.
- All other clinically significant non-hematological adverse event that is Grade 3 according to the NCI CTCAE version 5.0 will be DLTs.
- Myelosuppression and cytopenias are expected outcomes of leukemia treatment and *per se* will not constitute DLT. Only prolonged myelosuppression, as defined by the NCI criteria specific for leukemia, i.e. marrow cellularity < 5% with grade 4 neutropenia or thrombocytopenia on Day 42 or later from start of therapy without any evidence of leukemia, will be considered in defining DLT. In case of a normocellular bone marrow with no evidence of leukemia, 8 weeks with grade 4 neutropenia or thrombocytopenia will be considered a DLT. Anemia will not be considered for the definition of DLT.

Any patients who stop treatment prior to completing evaluation for the DLT observation period (first 28 days) due to disease progression or refusal for further participation for reasons other than

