toxicity during the DLT defining phase Ib portion of the study will be replaced for DLT evaluation. Patients who come off study earlier than 28 days during the DLT evaluation period may continue therapy off protocol if they are having clinical benefit, after discussion with the PI. The rationale for continuing therapy must be clearly documented in the patients chart.

Patients must receive at least 75% of the scheduled doses of quizartinib and at least 75% of the scheduled doses of venetoclax, respectively, in any given cohort to be eligible for DLT evaluation. Patients who receive <75% of the scheduled dose of either quizartinib or venetoclax will not be eligible for DLT evaluation and must be replaced. However, subjects who are unable to complete at least 75% of the prescribed dose of venetoclax and quizartinib in Cycle 1 (28 days) due to clinically significant non-hematologic adverse event or abnormal laboratory values that meet the definition of DLT in section 3.4 will be considered to have a DLT. Such patients may continue to receive protocol therapy if they are having clinical benefit, after discussion with the PI. The rationale for continuing therapy must be clearly documented in the patient's chart.

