Cardiac Toxicity	Grade 1 QTc ≥ 450 and ≤ 480 msec	Check magnesium and potassium levels and correct any abnormalities. If possible, stop any medications that may prolong the QTc interval. Continue quizartinib at the same dose.
Cardiac Toxicity	Grade 2 QTc > 480 and ≤ 500 msec	Check magnesium and potassium levels and correct any abnormalities. If possible, stop any medications that may prolong the QTc interval. The dose of quizartinib will be reduced one level without interruption of dosing. Following dose reduction, the quizartinib dose may be resumed at the previous level in the next cycle if the QTc has decreased to within 30 msec of baseline or <450 msec but subject must be monitored closely for QT prolongation for the first cycle at the increased dose. Subjects who experience >480 msec QTc prolongation and undergo dose interruption and/or reduction must be monitored closely with ECGs, performed twice weekly for the first week of the QTc prolongation and then weekly thereafter until the QTc prolongation is resolved.

Cardiac Toxicity	Grade 3 QTc interval >500 msec (at least on two separate EKGs) or >60 ms change from baseline	Check magnesium and potassium levels and correct any abnormalities. Interrupt quizartinib and if possible any medications that may prolong the QTc interval. Quizartinib dosing will be interrupted for up to 14 days. If QTcF returns to within 30 msec of baseline or <450 msec within 14 days, quizartinib administration may be resumed at a reduced dose (reduce by one level). Subjects who experience >500 msec QTcF prolongation and undergo dose interruption and/or reduction must be monitored closely with ECGs, performed twice weekly for the first week of the QTcF prolongation and then weekly thereafter until the QTc prolongation is resolved.
Cardiac Toxicity	Grade 4 , and Torsade de pointes or polymorphic ventricular tachycardia or signs/symptoms of serious arrhythmia (i.e., grade 4)	Quizartinib dosing will be permanently discontinued

- If the criteria to resume treatment are met, the subject should restart treatment at the next scheduled time point per protocol. However, if the treatment is delayed past the next scheduled time point per protocol, the next scheduled time point will be delayed until dosing resumes.

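### Section 3.4 and Table 2 disagree on whether a QTcF rise above 60 msec is a DLT, and the 75% dosing rule replaces patients under-dosed for drug toxicity short of a DLT, so the six-patient MTD count leans toward tolerability

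*Combined protocol and SAP*

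**What the plan says.** Section 3.4 opens by making clinically significant non-hematologic events of Grade 3 or higher in cycle 1 DLTs, subject to listed exceptions. QTc is one of the listed bullets: "Grade 3 QTc prolongation will constitute DLT as follows". The only Grade 3 trigger it gives is an absolute value: "If the QTcF is > 500 msec the EKG must be evaluated within 4 hours in triplicate", with persistence at Grade 3 or higher then counting as a DLT. The next bullet adds: "All other clinically significant non-hematological adverse event that is Grade 3 according to the NCI CTCAE version 5.0 will be DLTs".

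Table 2 in Section 5.2.2 defines the grade differently: "Grade 3 QTc interval >500 msec (at least on two separate EKGs) or >60 ms change from baseline". Its instruction is: "Quizartinib dosing will be interrupted for up to 14 days". Dosing resumes one level lower once QTcF is within 30 msec of baseline or below 450 msec.

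On evaluability, Section 3.4 says: "Patients who receive <75% of the scheduled dose of either quizartinib or venetoclax will not be eligible for DLT evaluation and must be replaced". A rescue sentence counts an under-dosed patient as a DLT, but only where the shortfall is "due to clinically significant non-hematologic adverse event or abnormal laboratory values that meet the definition of DLT in section 3.4". Section 3.3 is narrower: "Patients that are removed from study before day 28 for any reason other than toxicity and have not experienced DLT will be replaced".

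The MTD is the highest dose with at most one DLT in six patients (Sections 3.3 and 11.1). Phase II toxicity stopping (Section 11.2, Table 5) counts the same DLTs.

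**The concern.** There are two linked problems.

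First, one ECG finding can be scored two ways. Take a patient with a baseline of 420 msec who reaches 490 msec, a rise of 70. Table 2 calls this Grade 3 and stops quizartinib. The QTc bullet in Section 3.4 does not, because 500 msec was never exceeded. The lead sentence and the following bullet could bring it back in, since it is a Grade 3 event. Two investigators could score it differently and both cite the protocol.

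Second, the 75% rule has no carve-out for toxicity short of a DLT. Section 3.3 replaces patients who leave for reasons other than toxicity. The 75% rule replaces anyone under-dosed unless the event is already a DLT. A patient who could not stay on a drug because of that drug can be swapped for one who could.

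Both problems push the DLT count down at 60 mg, the target dose, where QTc is the known hazard of quizartinib.

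**Working it through.** **The plan's own figure.** The protocol gives no operating characteristics for the 2/6 rule. The nearest figure that uses the DLT definition is Table 6. Take true CRc 50%, true DLT rate 30%, and stopping at 4/5, 6/10 or 8/15 DLTs or at ≤2/10 or ≤4/15 CRc, with the two outcomes independent. The exact probability of stopping early is 1 − 0.9156 × 0.9169 = 0.1605, matching the printed value.

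**QTc rates at 60 mg (Section 2.2, monotherapy).** Above 500 msec: 3% of 38, taken as 1/38. Rise above 60 msec: 19%. The printed 44%, 36% and 19% fit 16, 13 and 7 of 36, so I use 7/36; 7/38 would round to 18%.

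**Chance that QTc events alone give two or more DLTs in six:** 1 − (1−p)^6 − 6p(1−p)^5.

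| What counts | p | P(≥2/6) |
|---|---|---|
| >500 msec only | 1/38 | 1 − 0.8521 − 0.1382 = 1.0% |
| Rise >60 msec, assumed cycle 1 rate | 5% | 1 − 0.7351 − 0.2321 = 3.3% |
| Rise >60 msec, assumed cycle 1 rate | 10% | 1 − 0.5314 − 0.3543 = 11.4% |
| Rise >60 msec, monotherapy maximum | 7/36 | 1 − 0.2733 − 0.3958 = 33.1% |

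The overlap between the two QTc criteria is not given. With none, p = 0.03 + 0.19 = 0.22 and the result is 39%. Substantial overlap is likely, because entry requires a baseline of at most 450 msec.

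**Adding an assumed, independent 10% rate of other DLTs**, p = 1 − 0.9(1 − q):
- q = 1/38: p = 0.124, P(≥2/6) = 16%
- q = 5%: p = 0.145, 21%
- q = 10%: p = 0.19, 32%
- q = 7/36: p = 0.275, 52%

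The Table 5 boundaries, by exact binomial, stop phase II for toxicity with probability 0.15% at p = 0.124 and 5.7% at p = 0.275.

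**When the 75% rule applies to quizartinib.** 21/28 = 75% and 20/28 = 71%, so eight missed doses make the patient non-evaluable. The hold must start by Day 21.

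**How long a hold should last.** Assume the QTcF effect falls with exposure, at the half-life of about 100 hours in Section 2.2. Resumption needs the rise to reach T = max(30, 450 − baseline), and the time is log2(rise/T) × 100/24 days.
- 420 to 490: log2(70/30) × 4.17 = 5.1 days
- 400 to 470: log2(70/50) × 4.17 = 2.0 days
- Longest case with a rise >60 and QTcF ≤500, over baselines 340–450: 420 to 500, log2(80/30) × 4.17 = 5.9 days, or six missed doses, 22/28 = 79%, still evaluable
- A hold beyond seven days needs a rise of 30 × 2^(168/100) = 96 msec from 420, or 516 msec, which if confirmed is a DLT anyway

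The expected path on the narrow reading is therefore a patient scored DLT-free. Replacement needs slower recovery or sparse rechecks. Above 480 msec, ECGs are required twice in the first week and then weekly, so a patient not recovered at one week could stay off drug until about day 14 of the hold.

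**The general case.** Venetoclax starts on Day 8, so cycle 1 schedules 21 doses. Missing six leaves 15/21 = 71%. A six-day hold for Grade 3 fatigue, which Section 3.4 exempts, would require replacement.

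**The case against.** The narrow reading has good support. Grade 3 QTc has its own bullet, so the bullet on other events naturally excludes it. Section 2.2 calls a QTc above 500 msec the dose-limiting toxicity of quizartinib and, for the first-in-human study, equates Grade 3 QTcF prolongation with values above 500 msec. Choosing that threshold is a legitimate design decision. This stands, but it does not settle the text. Section 2.2 also says that the frequency of rises above 60 msec at 90 mg and higher exceeded acceptable Grade 3 toxicity for an MTD. The narrow rule is also uneven: from a baseline of 420, a reading of 505 that repeats at 490 is still Grade 3 under Table 2 and so a DLT, while 490 at the first ECG never prompts the repeat.

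The 33% is also open to challenge. It uses maximum change on monotherapy, whereas here 60 mg begins on Day 12 at the earliest and only if QTcF is below 450 msec. That leaves at most 17 days in the DLT window. The objection stands, and 3–11% is the fairer illustration, though the combination's own rate is unknown.

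There are other safeguards. Grade 3 or higher QTcF events are recorded with a narrative (Section 10.4.1), all treated patients stay in the safety analysis (Section 11.3), the medical monitor reviews escalation (Section 3.2), and the RP2D may be set below the MTD. A reader might infer that these events vanish from the safety record. They do not; the gap is confined to the DLT count.

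**Conclusion.** The concern holds. The protocol does not say whether a QTcF rise above 60 msec with QTcF at or below 500 msec is a DLT. Its 75% rule replaces patients under-dosed for drug toxicity short of a DLT, which Section 3.3 would not do. Both act in the direction of calling the dose tolerable.

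From QTc events alone at 60 mg, the definition moves P(≥2/6) from 1.0% to 3–11% at assumed cycle 1 rates of 5–10%, and to about 33% at the monotherapy maximum-change rate. The effect on phase II stopping is smaller: 0.15% to at most 5.7% with 10% other DLTs. These figures assume independent patients and independent event types.

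Two stronger readings are not supported. A reader might infer that most patients with such a rise would be replaced. Under the half-life model with both Table 2 resumption routes, no such hold reaches eight doses, so replacement is possible but not the usual path. A reader might also infer that the 75% is measured in milligrams, because one sentence uses the singular. The governing sentence refers to the number of scheduled doses, and the 60 mg step-up is conditional, so a patient kept at 30 mg by the Day 12 check need not be regarded as under-dosed.

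**What to change.** Amend Section 3.4 as follows.

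(a) Define the QTc DLT once, in line with Table 2: QTcF above 500 msec, or a rise of more than 60 msec from the baseline triplicate mean, confirmed in triplicate within 4 hours.

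(b) Amend the 75% rule. A patient who falls below 75% of either drug because of a Grade 3 or higher study-drug-related non-hematologic toxicity, including a Table 2 Grade 3 QTcF hold, counts as a DLT and is not replaced. Replacement is limited to non-toxicity reasons, as in Section 3.3. The grade threshold keeps minor events from becoming DLTs. Say explicitly that an exempted Grade 3 event, such as fatigue, counts once it costs more than a quarter of the doses.

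(c) State that the 75% is counted in doses taken, and list every non-evaluable patient with the reason in the Toxicity Summary required by Section 11.3.

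The 2/6 rule and Tables 4 and 5 do not change. The cost is a few confirmatory triplicate ECGs and a somewhat higher chance that 60 mg is called above the MTD. In the randomized comparison in Section 2.2, CRc was 47% at both 30 mg and 60 mg, which limits what would be lost.

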3.5 Phase II expansion

Once MTD is defined, the RP2D will be selected based on efficacy, safety, and pharmacodynamics data evaluation from the phase Ib in discussion with the PI, Co-PI, sponsor and supporting companies (Daiichi-Sankyo, Abbvie and Genentech). The PI is responsible for completing the cohort summary template prior to advancing subjects to the phase II portion. The phase II portion will have 20 patients. Any patients still on study from the phase I portion at a dose lower than RP2D can be dose escalated up to RP2D in accordance with the dose escalation guidelines in section 5.2.3.

However, the dose for any patient may never exceed the RP2D.

4.0 PATIENT SELECTION

Patients must have baseline evaluations performed prior to the first dose of study drug and must meet all inclusion and exclusion criteria. Results of all baseline evaluations, which assure that all inclusion and exclusion criteria have been satisfied, must be reviewed by the Principal Investigator or his/her designee prior to enrollment of that patient. In addition, the patient must be thoroughly informed about all aspects of the study, including the study visit schedule and required evaluations and all regulatory requirements for informed consent. The written informed consent must be obtained from the patient prior to initiating treatment or any study-specific procedures. The following criteria apply to all patients enrolled onto the study unless otherwise specified.

4.1 Inclusion Criteria:

A subject will be eligible for study participation if he/she meets the following criteria within 14 days prior to the first day of therapy.

1. FLT3-ITD mutated patients with relapsed/refractory AML (up to four prior therapeutic regimens for AML i.e. up to salvage 4 AML), including patients who may have been previously exposed to prior FLT3-inhibitor/s other than quizartinib (SCT or stem cell therapy for patients who previously underwent SCT/stem cell therapy in remission will not be considered a salvage regimen).
2. Patients must be ≥ 18 .
3. Eastern Cooperative Oncology Group (ECOG) Performance status of 0 to 2.
4. Potassium, magnesium, and calcium (normalized for albumin) levels should be within institutional normal limits.
5. Adequate hepatic (serum direct bilirubin $\leq 1.5 \times$ upper limit normal (ULN) (or $\leq 3.0 \times$ ULN if deemed to be elevated due to leukemia), alanine aminotransferase and/or aspartate transaminase $\leq 2.5 \times$ ULN (or $\leq 5.0 \times$ ULN if deemed elevated due to leukemia). Note: Subjects with documented Gilbert's Syndrome may have a total bilirubin $> 1.5 \times$ ULN.
6. Adequate renal function as demonstrated by a serum creatinine ≤ 1.8
7. Patients must provide written informed consent.
8. With the exception of patients with rapidly proliferative disease, the interval from prior treatment to time of initiation of venetoclax and quizartinib administration will be at least 14 days or at least 5 half-lives (whichever is shorter) for cytotoxic/noncytotoxic agents. Patients with rapidly proliferative disease will not be required to wait for a washout and can start therapy at any time. The half-life for the therapy in question will be based on published pharmacokinetic literature (abstracts, manuscripts, investigator brochure's, or drug-administration manuals) and will be documented in the protocol eligibility document. The use of chemotherapeutic or anti-leukemic agents is not permitted during the study with the following exceptions: (1) intrathecal (IT) therapy for patients with controlled CNS leukemia at the discretion of the PI. Controlled CNS leukemia is defined by the absence of active clinical signs of CNS disease and no evidence of CNS leukemia on the most recent 2 simultaneous CSF evaluations. (2) Use of one dose of cytarabine (up to 2 g/m^2) or hydroxyurea for patients with rapidly proliferative disease is allowed before the start of study therapy and on therapy. These medications will be recorded in the case-report form.
9. Baseline ejection fraction by ECHO or MUGA must be $\geq 50\%$.
10. Women of non-childbearing potential are those who are postmenopausal greater than 1 year or who have had a bilateral tubal ligation or hysterectomy..

11. Women of childbearing potential must agree to have a negative serum or beta human chorionic gonadotropin (Beta-hCG) pregnancy test result within 7 days prior to the first dose of study drugs and must agree to use an effective contraception method during the study and for 90 days following the last dose of the study. Men who have partners of childbearing potential must agree to use an effective contraceptive method during the study and for 90 days following the last dose of study drug.

4.2 Exclusion Criteria

1. Subject has t(8;21) or inv(16) karyotype abnormalities.
2. Subject has acute promyelocytic leukemia (French-American-British Class M3 AML).
3. Prior exposure to quizartinib at any time in the past.
4. Serum potassium < 3.5 mEq/L despite supplementation, or > 5.5 mEq/L. Serum magnesium above or below the institutional normal limit despite adequate management. Serum calcium (corrected for albumin levels) above or below institutional normal limit despite adequate management.
5. Patients with known allergy or hypersensitivity to quizartinib, venetoclax or any of their components.
6. Subject with a known history of being HIV positive (due to potential drug-drug interactions between antiretroviral medications and venetoclax, as well as anticipated venetoclax mechanism-based lymphopenia that may potentially increase the risk of opportunistic infections). Note: HIV testing is not required.
7. Subject has consumed grapefruit, grapefruit products, Seville oranges (including marmalade containing Seville oranges) or Star fruit within 3 days prior to the initiation of study treatment.
8. Subject has a significant history of renal, neurologic, psychiatric, endocrinologic, metabolic, immunologic, hepatic, cardiovascular disease, or any other medical condition that in the opinion of the investigator and/or the PI would adversely affect his/her participating in this study. Patients who have had any major surgical procedure within 14 days of Day 1.
9. Subject has a malabsorption syndrome or other condition that precludes enteral route of administration.
10. Subject exhibits evidence of other clinically significant uncontrolled condition(s) including, but not limited to:
 - a. Uncontrolled systemic infection requiring IV therapy (viral, bacterial or fungal). Infections controlled on concurrent anti-microbial agents are acceptable, and anti-microbial prophylaxis per institutional guidelines is acceptable. Patients with neutropenic fever considered infection related should be afebrile for at least 72 hours prior to first dose.

11. Subject has a history of other malignancies within 1 year prior to study entry, with the exception of:
 - a. Adequately treated in situ carcinoma of the cervix uteri or carcinoma in situ of breast;
 - b. Basal cell carcinoma of the skin or localized squamous cell carcinoma of the skin;
 - c. Previous malignancy confined and surgically resected (or treated with other modalities) with curative intent.
 - d. Patients on active antineoplastic or radiation therapy for a concurrent malignancy, with curative or palliative intent, at the time of screening. Maintenance therapy, hormonal therapy, or steroid therapy for well-controlled malignancy is allowed.
12. Patients with a known positive hepatitis B or C infection by serology, with the exception of those with an undetectable viral load within 3 months (hepatitis B or C testing is not required prior to study entry). Subjects with serologic evidence of prior vaccination to HBV [i.e., HBs Ag-, and anti-HBs+] may participate.
13. Female subjects who are pregnant or breastfeeding.
14. Impaired cardiac function including any of the following:
 - Screening ECG with a QTc >450 msec. The QTc interval will be calculated by Fridericia's correction factor (QTcF) at Screening and on Day 1 prior to the first dose of quizartinib. The QTcF will be derived from the average QTcF in triplicate. If QTcF >450 msec on Day 1, quizartinib will not be given.
 - Patients with congenital long QT syndrome
 - History or presence of sustained ventricular tachycardia requiring medical intervention within 3 months prior to starting study drug
 - Any history of clinically significant ventricular fibrillation or torsades de pointes
 - Known history of second or third degree heart block (may be eligible if the patient currently has a pacemaker) within 3 months prior to starting study drug
 - Sustained heart rate of <50/minute on screening or Day 1 ECG
 - Right bundle branch block + left anterior hemiblock (i.e. bifascicular block). Isolated RBBB will not be an exclusion criterion.
 - Complete left bundle branch block
 - Patients with myocardial infarction or unstable angina within 6 months prior to starting study drug
 - CHF NY Heart Association class III or IV within 3 months prior to starting study drug

-Atrial fibrillation documented within 2 weeks prior to first dose of study drug.

-Patients who are actively taking CYP3A inducers. CYP3A4 inducers should be stopped at least 3 days prior to the first dose of quizartinib and are prohibited at any time on study

